7 RESEARCH METHODS

7.1 Study Design

This is a prospective observational cohort study evaluating the effectiveness and safety of belzutifan for patients newly assigned to belzutifan treatment ('new users') in routine clinical practice. The study has been designed with procedures to obtain data consistently and accurately in alignment with associated quality assurance principles defined for registries⁸. Timepoints for visits/assessments are not pre-specified by the protocol. All patient encounters will be performed according to the routine clinical practice at participating sites. Given the rare nature of VHL disease, the study will be conducted across several regions, commencing initially at clinical sites in the United States. As needed, additional countries and sites will be evaluated for inclusion once local marketing authorization is obtained and reimbursement for cost of the drug is available. The ability to leverage existing national registries for VHL data collection will be evaluated on a case by case basis.

During the recruitment period, once the treatment decision for use of belzutifan has been made by the patients' physician (at his/her own discretion), patients will be approached regarding study participation. Patients who meet the eligibility criteria and consent to participate prior to or within 30 days after the first initiation of belzutifan will be enrolled. Date of first administration of belzutifan will be defined as the index date for the patient. Patients will be treated per the approved product label. Baseline characteristics that are collected will include, but not be limited to, demographics, pre-existing conditions, baseline tumor characteristics, prior oncologic/VHL therapies and medications. Data reported on the index date or subsequent follow-up visits per the local standard of care will be captured by the site in case report forms (CRFs) using an electronic data capture (EDC) system (see Section 7.6).

Patients will be followed from enrollment and treatment until the end of observation, defined as the earliest of withdrawal of consent, loss to follow-up, death, or until the end of the study. The planned minimum follow-up for each patient will be 3 years, noting that with a median duration of treatment follow-up of 2.4 years in the pivotal trial (MK-6482-004)², the majority of surgeries and reports of disease progression occurred within ~3 years of treatment, and the highest exposure-adjusted event rate occurred within 3 months of treatment. The non-interventional study duration considers the feasibility of running a long-term prospective observational cohort study while maintaining scientifically robust assessments. With a planned enrollment of patients within 2-3 years, the planned maximum follow-up for patients in the registry will be up to 5-6 years.

Up to 100 patients with VHL disease-associated RCC, CNS hemangioblastoma or pNET will be enrolled in the registry. This includes approximately 40 patients with VHL disease-associated RCC and approximately 40 patients with VHL disease-associated CNS

² 15-Jul-2021 database lock

	2
PRODUCT: MK-6482	PROTOCOL/AMENDMENT VERSION NO.: 6482-026/3.0
REVOPS ID NO: NIS102327	CORE DRC APPROVAL DATE: 28-NOV-2023
EPIDEMIOLOGY NO. (PE STUDIES ONLY): EP05047.006	CRC PRC APPROVAL DATE: N/A

hemangioblastoma that require treatment per investigator's judgment for the primary effectiveness analysis. Minimal attrition is expected during the duration of the study as most patients will likely remain under the care of the treating physician, as observed for patients in the MK-6482-004 clinical trial (~90% of participants still on study with a median duration of \sim 3 years) given that these sites provide specialized care for patients with VHL disease. Enrollment will be closely monitored during the enrollment period and enrollment of patients with each VHL disease-associated tumor type (RCC, CNS hemangioblastoma) will be stopped once the target sample size for that tumor type is reached with overall recruitment into the registry stopped once the sample size requirement for both tumor types is met. As one patient can have both RCC and CNS hemangioblastoma requiring treatment, each would contribute to the required sample size for that tumor type. If this were to occur, it would result in less than 80 patients included in the effectiveness analysis. All eligible patients receiving belzutifan treatment (including those patients with VHL disease-associated pNET) will be included in the safety analysis.

Effectiveness analyses will be restricted to patients with VHL disease-associated RCC and/or VHL disease-associated CNS hemangioblastoma given these are the most common clinical manifestations and are associated with the greatest morbidity and mortality. All patients enrolled in the registry will be included in the safety analysis.

7.2 Setting

This prospective observational cohort study will be conducted at participating clinical sites within the US. Potential patients at participating clinical sites will be approached about study participation once the treatment decision with belzutifan is made by the treating physician. Patients who fail Screening may be rescreened for eligibility after consultation between the investigator and the Sponsor.

7.2.1 Inclusion Criteria

Patients will be included if they meet the following criteria at the index date³:

- 1. ≥ 18 years of age.
- 2. Diagnosed with VHL disease based on a germline test or clinical diagnosis.
- 3. A decision has been made by the treating physician (at his/her discretion) to initiate the first belzutifan treatment (i.e., belzutifan 'new users'), within the prescribing conditions of the approved product label.
- 4. Signed informed consent prior to or within 30 days after the first initiation of belzutifan.

³ index date for the patient is defined as the date of first administration of belzutifan

PRODUCT: MK-6482	PROTOCOL/AMENDMENT VERSION NO.: 6482-026/3.0
REVOPS ID NO: NIS102327	CORE DRC APPROVAL DATE: 28-NOV-2023
EPIDEMIOLOGY NO. (PE STUDIES ONLY): EP05047.006	CRC PRC APPROVAL DATE: N/A

7.2.2 Exclusion Criteria

- 1. Anti-cancer systemic therapy within 2 weeks prior to the index date.
- 2. Unable to consent to participate in the study.
- 3. History of VHL disease-related metastasis or advanced cancer.

7.3 Variables

Variables (exposures, outcomes, and other study variables) are defined in this section. See Section 7.4.1 for data collection timing.

7.3.1 Exposure

Treatment initiation and subsequent dose modification will be at the discretion of the treating physician. Exposure will be documented from the date the patient received a first dose of belzutifan (index date).

Primary exposure definition: Patients included in this registry will be considered exposed to belzutifan if they receive at least one dose. Participants will be followed until the end of observation, defined as the earliest of withdrawal of consent, loss to follow-up, death, or until the end of the study.

For the analysis of safety, patients will be considered as treated for up to 90 days after discontinuation of therapy or 30 days after a treatment switch.

Data captured on belzutifan treatment exposure, e.g.,:

- Start date, starting dose, duration of therapy
- As applicable, treatment interruption, reason for interruption, and date that drug was resumed
- As applicable, treatment discontinuation and reason for discontinuation
- As applicable, dose reduction and reason for dose reduction

7.3.2 Outcomes

The primary effectiveness outcome is the proportion of patients who undergo surgery or other tumor reductive procedure. Reason for surgery and tumor characteristics preceding surgery will also be collected.

The secondary effectiveness outcomes include:

1. Metastatic disease (RCC only)

	23
PROTOCOL/AMENDMENT VERSION NO.: 6482-026/3.0	
CORE DRC APPROVAL DATE: 28-NOV-2023	
CRC PRC APPROVAL DATE: N/A	
	PROTOCOL/AMENDMENT VERSION NO.: 6482-026/3.0 CORE DRC APPROVAL DATE: 28-NOV-2023 CRC PRC APPROVAL DATE: N/A

- 2. Treatment patterns (e.g., duration of use, proportion of patients who interrupt, reasons for interruption) will be evaluated using data captured on belzutifan treatment exposure.
- 3. Occurrence of new VHL disease-associated RCC, CNS hemangioblastoma, pNET or other VHL disease-associated tumor type (pheochromocytoma, paraganglioma, retinal hemangioblastoma, endolymphatic sac tumor)

During follow-up, data on all new tumor types and number of lesions will be collected and all VHL disease-associated procedures, anti-cancer medications, and concomitant medications will be collected. If available, best response to treatment per local radiology assessment for primary tumors will be also captured at the time of belzutifan discontinuation.

Safety outcomes will include SAEs (including fatal outcome) as well as the nature of these events.

Any herein described health outcomes, collected per the protocol, will be summarized as part of any interim analysis (if required) and in the final study report in addition to being reported in real-time as individual adverse events (AEs)/product quality complaints (PQCs) if the criteria in Section 9 are met. Refer to Section 9 for AE reporting requirements and procedures.

7.3.3 Other Study Variables

Patients' demographics, including:

- 1. Age (at index date)
- 2. Sex
- 3. Race and ethnicity
- 4. Height and weight
- 5. Country of residence

Clinical characteristics will include general medical history, history of VHL diagnosis, primary VHL disease-associated tumor(s), prior oncologic treatment, and other baseline measures. Specifically, the following measures will be collected:

General medical history, including:

- 1. Family history of VHL disease
- 2. History of cancer, cancer type, metastasis

PRODUCT: MK-6482	PROTOCOL/AMENDMENT VERSION NO.: 6482-026/3.0
REVOPS ID NO: NIS102327	CORE DRC APPROVAL DATE: 28-NOV-2023
EPIDEMIOLOGY NO. (PE STUDIES ONLY): EP05047.006	CRC PRC APPROVAL DATE: N/A

- 3. Comorbidities (e.g., diabetes, hypertension, anemia, pulmonary disease, history of heart failure, history of coronary artery disease)
- 4. Concomitant medications

History of VHL diagnosis, including:

- 1. Age at VHL diagnosis
- 2. Genetic confirmation of VHL diagnosis
- 3. Clinical confirmation of VHL diagnosis
- 4. VHL mutation variant (amplification/gain, deletion, duplication, fusion, indel, partial deletion, rearrangement/translocation, single nucleotide variant, small insertion)

Information on VHL disease-associated tumor(s) at index date, including:

1. Primary tumor type(s) requiring belzutifan treatment (RCC, CNS hemangioblastoma, pNET). In the data entry guidelines, the physician will be instructed to document if the patient is being treated for a single VHL tumor type (e.g. RCC) or multiple VHL tumor types (e.g. RCC and CNS hemangioblastoma).

For RCC, CNS hemangioblastoma, and/or pNET

- 2. Date of tumor diagnosis
- 3. Stage of primary tumor(s) (T, N, M staging, defined by Staging Classification System (American Joint Committee on Cancer [AJCC])
- 4. Grade of primary tumor(s), if available (e.g., RCC, pNET)
- 5. Location (i.e., RCC: left, right; CNS hemangioblastoma: cerebellum, spine, other; pNET: head, body/tail)
- 6. Number of tumors
- 7. Longest diameter
- Presence of other VHL disease-associated tumors (pheochromocytoma, paraganglioma, retinal hemangioblastoma, endolymphatic sac tumor) and number of lesions

Prior oncologic treatment, including:

1. Systemic therapy

PRODUCT: MK-6482	PROTOCOL/AMENDMENT VERSION NO.: 6482-026/3.0
REVOPS ID NO: NIS102327	CORE DRC APPROVAL DATE: 28-NOV-2023
EPIDEMIOLOGY NO. (PE STUDIES ONLY): EP05047.006	CRC PRC APPROVAL DATE: N/A

25

- 2. Surgery for primary VHL disease-associated tumor(s) (partial nephrectomy, nephrectomy, craniotomy, partial pancreatectomy, pancreatectomy, other [specify])
- 3. Procedures for reduction of primary VHL disease-associated tumors (radiofrequency ablations, laser ablations, cryotherapy, cryoablations, radiation therapy, other [specify])
- 4. Other VHL related surgeries

Other baseline and follow-up measures:

- 1. Hemoglobin
- 2. Oxygen saturation percentage by pulse oximetry
- 3. Blood pressure
- 4. Behavioral risk factors (alcohol use [current, recent, abstain], smoking habits [current, recent, former]) (baseline only)
- 5. Estimated glomerular filtration rate (baseline only, RCC patients)

The data collected on these pre-defined events will include as much detail as is available within each patient's record, including but not limited to histopathologic results, and relevant laboratory and imaging results.

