For observational studies, it is accepted that data could be missing or incomplete per the physician records. Incomplete and missing electronic CRF data will be flagged and collected as part of ongoing data quality monitoring in the study. Where information is not available, trained personnel or the study coordinator who are completing the electronic CRFs will be able to click a checkbox which records these data as 'Not Available'. Clicking this checkbox will lock all related fields in the form, thus reducing the probability of missing queries. Incomplete and missing electronic CRF data not related to critical data items will be flagged as non-critical or queried as 'Not Available' or 'Unknown' in the electronic CRF.

PRODUCT: MK-6482	PROTOCOL/AMENDMENT VERSION NO.: 6482-026/3.0
REVOPS ID NO: NIS102327	CORE DRC APPROVAL DATE: 28-NOV-2023
EPIDEMIOLOGY NO. (PE STUDIES ONLY): EP05047.006	CRC PRC APPROVAL DATE: N/A

Patient-level data for all patients enrolled in the study will be provided proactively by participating sites and will be anonymized. During the study, the MAH or designee may make site visits to review protocol compliance, compare electronic CRFs and individual patient's medical records to ensure that the study is being conducted according to pertinent regulatory requirements. Checking of the electronic CRFs for completeness and clarity, and cross-checking with source documents, may be required to monitor the progress of the study. Moreover, regulatory authorities of certain countries, IRBs/ IECs, and/or the Sponsor's Clinical Quality Assurance Group may wish to carry out source data checks and/or on-site audit inspections. Direct access to source data will be required for these inspections and audits; they will be carried out given due consideration to data protection and medical confidentiality.

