7.7.1 General Consideration

All statistical analyses will be performed using Statistical Analysis System[®] (Cary, North Carolina version 9.4 or higher) unless otherwise stated. No formal statistical hypothesis testing will be performed, and all the analyses will be primarily descriptive in nature. When appropriate, and unless otherwise specified, 95% confidence intervals (CIs) will be displayed.

	3	31
PRODUCT: MK-6482	PROTOCOL/AMENDMENT VERSION NO.: 6482-026/3.0	
REVOPS ID NO: NIS102327	CORE DRC APPROVAL DATE: 28-NOV-2023	
EPIDEMIOLOGY NO. (PE STUDIES ONLY): EP05047.006	CRC PRC APPROVAL DATE: N/A	

A 95% exact binomial CI (based on Clopper and Pearson method) will be calculated for proportion outcomes (e.g., primary outcome proportion of patients who undergo surgery or locally directed therapy).

Descriptive statistics will include the number of available data, number of missing data and the following:

- Mean, standard deviation (SD), minimum, median, maximum, first and third quartiles and 95% CIs for means/medians.
- Counts and percentages of each category for categorical variables with 95% CIs.

Percentages will be based on the number of non-missing observations.

Missing data will not be replaced. Imputation rules will be detailed in the SAP, as appropriate (e.g., for incomplete dates).

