7.7.3.1 Demographic and Other Baseline Characteristics

Demographic and clinicopathological characteristics will be tabulated and reported using mean, SD, median, minimum, and maximum for continuous variables; numbers and percentages for each category will be provided for categorical variables.

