7.9 Limitations of the Research Methods

Limitations of this prospective observational cohort study and how they will be addressed are summarized in Table 3.

As this is a real-world study with patients treated under routine clinical practice, patients may be lost to follow-up. Those patients who are lost to follow-up may have different clinical and demographic characteristics than those who remain in the study leading to bias of the study results.

	34
PRODUCT: MK-6482	PROTOCOL/AMENDMENT VERSION NO.: 6482-026/3.0
REVOPS ID NO: NIS102327	CORE DRC APPROVAL DATE: 28-NOV-2023
EPIDEMIOLOGY NO. (PE STUDIES ONLY): EP05047.006	CRC PRC APPROVAL DATE: N/A

Potential Limitation	Description	Mitigation
Enrollment uncertainty	VHL is a rare disease with an evolving treatment landscape which may pose challenges in enrollment.	Feasibility assessments of sites will be performed to identify those sites with adequate projected patient counts. Enrollment will be closely monitored and extended to additional sites and countries, as required and feasible.
Selection bias	External validity: Patients who enroll in this study may not be generally representative of the overall VHL population (e.g., patients prescribed belzutifan may have different disease prognosis) Internal validity: As this is a real-world study with patients treated under routine clinical practice, patients may be lost to follow-up. Those patients who are lost to follow-up may have different clinical and demographic characteristics than those who remain in the study leading to bias of the study results.	Patients will be enrolled from different sites. An evaluation of patient clinical and demographic characteristics will inform the assessment of the extent of selection bias.
Unmeasured risk factors for study outcomes	There may be unmeasured clinical or demographic characteristics that are related to the study outcomes impacting the interpretation of the effectiveness or safety outcomes.	To the extent possible, known clinical and demographic factors related to the study outcome will be collected from the patients' medical record. If a clinically meaningful unmeasured factor is identified, the feasibility of sensitivity analyses to determine the impact will be explored.

Table 3Limitations of the Research Methods

	35
PRODUCT: MK-6482	PROTOCOL/AMENDMENT VERSION NO.: 6482-026/3.0
REVOPS ID NO: NIS102327	CORE DRC APPROVAL DATE: 28-NOV-2023
EPIDEMIOLOGY NO. (PE STUDIES ONLY): EP05047.006	CRC PRC APPROVAL DATE: N/A

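### The smoking item in protocol section 7.3.3 has no never-smoker level; if the eCRF follows the list, every patient with a coded smoking status would be shown as a current or past smoker.

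*Protocol*

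**What the plan says.** Section 7.3.3 (Other Study Variables) gives the levels of two behavioral risk factors, both collected at baseline only. Smoking is "smoking habits [current, recent, former" and alcohol is "alcohol use [current, recent, abstain". The smoking list contains neither an 'e.g.' nor an 'other' level; the prior surgery and procedure items in the same section do end with an open 'other'. The Abstract and Table 1 name smoking without giving levels, so 7.3.3 is the only place where they are set out.

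Four further statements decide how the item would be reported:

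- Section 7.7.1, denominator: "Percentages will be based on the number of non-missing observations".
- Section 7.7.1, missing values: "Missing data will not be replaced". The same section also says "Descriptive statistics will include the number of available data, number of missing data and the following", so the missing count is displayed.
- Section 7.7.3.1, baseline table: "numbers and percentages for each category will be provided for categorical variables".
- Section 7.6, when the chart lacks the information: the person completing the form "will be able to click a checkbox which records these data as 'Not Available".

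**The concern.** All three smoking levels describe someone who smokes or has smoked. A site that uses the list as written has no correct entry for a never-smoker. The contrast with the alcohol item, which does have a no-use level, suggests an oversight rather than a choice.

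This is not something a statistical analysis plan can put right by itself, because an analysis cannot restore a level that was never offered at data entry. At stake is the accuracy of one line of the baseline table. Table 3 in section 7.9 gives that table a purpose: "An evaluation of patient clinical and demographic characteristics will inform the assessment of the extent of selection bias". Smoking is one of many characteristics covered by that sentence.

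**Working it through.** The plan states no figure for smoking, so there is nothing to reproduce. The check is what the table would print if the eCRF used the three levels in 7.3.3 and no others.

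**Inputs from the protocol.** The three levels (7.3.3); percentages over non-missing values, with no replacement (7.7.1); about 40 patients per tumor type and up to 100 overall (7.5).

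**Assumptions.** The protocol gives no never-smoker share, so 30% to 70% is used. An entry of not available is counted as missing.

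**Formulas.** Let N be the number of patients, V the never-smokers, and f the fraction of never-smokers misfiled as former; the rest are missing.

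- True ever-smoker share = (N − V) / N.
- Non-missing count = (N − V) + fV.
- Displayed ever-smoker share = [(N − V) + fV] / [(N − V) + fV] = 100% for any f.
- Missing count caused by never-smokers = (1 − f)V.

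**Results with f = 0** (all never-smokers missing):

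| N | Assumed never | Non-missing | Missing | True ever | Displayed ever |
|---|---|---|---|---|---|
| 40 | 30% | 28 | 12 | 70% | 100% |
| 40 | 50% | 20 | 20 | 50% | 100% |
| 40 | 70% | 12 | 28 | 30% | 100% |
| 100 | 30% | 70 | 30 | 70% | 100% |
| 100 | 50% | 50 | 50 | 50% | 100% |
| 100 | 70% | 30 | 70 | 30% | 100% |

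**Effect on single levels.** Assume 40 patients: 24 never, 6 current, and 40 − 24 − 6 = 10 recent or former. The true shares are 6/40 = 15% current and 10/40 = 25% recent or former.

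- f = 0: current is displayed as 6/16 = 37.5%, and recent or former as 10/16 = 62.5%, with 24 missing.
- f = 1: current is displayed correctly as 6/40 = 15%, but recent or former becomes (10 + 24)/40 = 34/40 = 85%, with none missing.

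So the missing count shows the problem when f = 0 and is silent when f = 1.

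**The case against.** The strongest reply is that section 7.3.3 describes variables and is not the eCRF. Section 7.6 has the forms designed by a multifunctional team and put through user acceptance testing, with a data dictionary, validation rules and entry guidance. A never-smoker level may already exist there. This stands, and the point is therefore conditional on the eCRF following the protocol list. It does not make the list in 7.3.3 complete.

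Second, the missing count would be printed next to the percentages, and 24 missing of 40 would be hard to overlook. This also stands, in part. The count would not separate never-smokers from patients whose status is truly unknown, and it gives no signal for those misfiled as former.

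Third, a reader might infer several stronger things that the protocol does not support:

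- *That the error could never be repaired.* The source is the medical record (7.4), queries run regularly and forms may be checked against source (7.6), and planned follow-up is at least 3 years (7.1). Charts could be re-abstracted, at some cost.
- *That a comparison with the natural history cohort would be spoiled.* Nothing says that this cohort recorded smoking or that smoking will be compared. Section 7.7.4 benchmarks only the number and proportion of patients having procedures.
- *That the assessment of selection bias depends on smoking.* It is one item among many. For patients who decline consent, only age, sex and the reason may be collected (7.7.3.2), so smoking cannot inform that contrast however it is coded.
- *That 'recent' is an error and should be dropped.* Keeping it is a legitimate choice; it needs only a cut-off against 'former', which belongs in the entry guidance.

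**Conclusion.** The point holds as a minor correction. The smoking list in 7.3.3 is incomplete, and no other part of the protocol supplies the missing level. If the eCRF carries the same list, the displayed ever-smoker share is 100% of coded patients regardless of the truth. Under the assumed 30% to 70% never-smokers, that overstates the share by 30 to 70 percentage points. The size rests on that assumed range; the 100% itself does not, provided that not available counts as missing.

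It would go too far to say that the registry will report a cohort made up entirely of ever-smokers: the eCRF is not shown, and the missing count may reveal the gap. Smoking enters no objective, no named outcome analysis and no sample-size figure, so the primary proportions and their exact confidence intervals are untouched.

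**What to change.** 1. In section 7.3.3, add 'never' to the smoking levels.
2. Confirm that the eCRF code list and data dictionary contain the same level, kept distinct from 'Not Available' and 'Unknown'.
3. If any baseline forms were completed without it, query the blank, not-available and former entries against the chart.
4. State the cut-off between 'recent' and 'former' in the data entry guidance; the protocol need not carry it.

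The cost is one line of protocol text and one code-list entry if the eCRF lacks the level, plus a short round of queries if data entry has begun. No new assessment is asked of patients, and information that is not in the chart stays not available.
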